# 7. Study Patients/Subjects and Demographics

# 7.1. Disposition of Patients/Subjects and Withdrawals

A summary of the analysis sets includes the number and percentage of subject's rollover and in the safety population. All percentages will be based on the safety population.

The following will be summarized by treatment group:

- Number of participants who enrolled,
- Number and percentage of participants in safety analysis set,
- Number and percentage of participants who completed the study, and
- Number and percentage of participants who discontinued from the study, including the reason for study discontinuation.

# 7.2. Demographics and Other Baseline Characteristics

Demographic and baseline characteristics [age, sex (including child-bearing potential for women), methods of contraception, race, ethnicity, weight, height, body mass index (BMI), and education level] will be summarized by treatment group using the descriptive statistics.

Height and weight will be measured at Study Day 1 and then the BMI will be calculated at Study Day 1. If height is missing in Study Day 1 then the pivotal studies screening visit height and Study Day 1 weight will be used for BMI calculation. Individual subject demographics and baseline characteristics will be provided in listings.

For the continuous variables, the number of non-missing values and the mean, standard deviation, minimum, median and maximum will be tabulated.

For the categorical variables, the count and percentage of each value will be tabulated.

These analyses will be conducted for the Safety populations.

# 7.3. Exposure and Compliance

# 8. Efficacy Analysis

# 8.1. Primary Efficacy Analysis

No applicable Primary Efficacy Analysis is planned.

# 8.2. Secondary Efficacy Analysis

No applicable Secondary Efficacy Analysis is planned.

# 9. Safety and Tolerability Analysis

All safety analyses will be performed on the safety analysis set.

Safety will be evaluated from reported AEs. No inferential statistical tests will be performed, unless otherwise specified.

For all safety and tolerability analyses, participants will be analyzed by the actual treatment.

All safety and tolerability data will be presented in listings.

[figure not shown]

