#### 3.4. Treatments Administered

All participants received simufilam 100 mg tablets BID.

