# 4. Statistical Analysis and Reporting

# 4.1. Introduction

Data processing, tabulation of descriptive statistics, calculation of inferential statistics, and graphical representations will primarily use SAS (release 9.4 or higher). If the use of other software

is warranted, the final statistical methodology report will detail what software was used for what purposes.

Descriptive summaries of variables will be provided where appropriate. Continuous (quantitative) variable summaries will include the number of subjects (n) with non-missing values, mean, standard deviation (SD), median, minimum, and maximum.

Categorical (qualitative) variable summaries will include the frequency and percentage of subjects who are in the category for each value. In general, the denominator for the percentage calculation will be based upon the total number of subjects in the study population for the treatment group (or cohorts), unless otherwise specified.

The minimum and maximum will be reported with the same degree of precision (i.e., the same number of decimal places) as the observed data. Measures of location (mean and median) will be reported to 1 degree of precision more than the observed data and measures of spread (SD) will be reported to 2 degrees of precision more than the observed data.

Percentages will be presented to 1 decimal place, unless otherwise specified.

This study is considered an exploratory study. Statistical tests will be interpreted in an exploratory sense only and will not be considered formal hypothesis tests.

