# 6. General Issues for Statistical Analysis

# **6.1.** Statistical Definitions and Algorithms

#### 6.1.1. Baseline

The last observation recorded before the first dose of treatment will be used as the baseline observation. The clinical and laboratory assessments performed at the Week 76 (PTI-125-06) or Week 52 (PTI-125-07) End-of-Treatment visit will serve as the baseline (Study Day 1) for this open-label extension study. In the event the End-of-Treatment visit and the Study Day 1 visit for the open-label extension study did not occur on the same date, the Medical Monitor was responsible for deciding whether any clinical and laboratory assessments needed to be repeated to

serve as baseline values for Study Day 1 depending upon the length of time between the two visits.

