# 6.1.6. Data Adjustments/Handling/Conventions

[figure not shown]
Only limited data required for analysis will be presented in listings or Clinical Data Interchange Standards Consortium (CDISC) datasets. Analysis results will be presented and summarized in either tables and/or listings. Data not subject to analysis according to this plan will not appear in any tables and listings.

The version 24.0 of the Medical Dictionary for Regulatory Activities (MedDRA) will be used to classify all AEs by system organ class (SOC) and preferred term (PT).

Ongoing AEs from the pivotal studies will be classified as TEAEs in the current study only if they increase in severity on or after the date of the first dose of study drug in the current study. Otherwise, they will be classified as medical history events.

Adverse events with entirely missing start dates will be classified as treatment-emergent, as appropriate.

For partial AE start dates: (a) if only the day is missing, and the month and year match the first dose date and the end date is on or after the first dose date, or AE is ongoing, then the date is assigned the first dose date thus the event will be considered as treatment-emergent; if the month and/or year do not match the first dose date or the end date is prior to the first dose date, then the day is assigned the first day of the month (01); (b) if month or the day and month are missing, and the year matches the first dose date and the end date is on or after the first dose date, or AE is ongoing, then the date is assigned the first dose date; if the year does not match the first dose date

or the end date is prior to the first dose date, then the day/month are assigned the first day of the year (01JAN).

For partial end dates: (a) if only the day is missing, then the day is assigned the last day of the month; (b) if both day and month are missing, they are assigned the last day of the year (31DEC).

Participants will be analyzed by the treatment received for all safety and tolerability assessments.

A treatment related AE is any AE with a relationship to the study drug of "Possibly Related" or "Probably Related" or "Reasonable Possibility".

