#### 9.1. Adverse Events

An AE is any undesirable event that occurs to a participant during a study, whether that event is considered related to Study Drug.

All summaries of AEs will be based on treatment-emergent adverse events (TEAEs) unless specified otherwise.

An adverse event is considered a TEAE if:

• The adverse event first occurred on or after the date of the first dose of study drug; or

• The adverse event was before the date of the first dose of study drug, but it increased in severity or became serious on or after the date of the first dose of study drug.

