#### 9.1.4. Summaries of Adverse Events

An overall summary of TEAEs will be provided by treatment. This summary will present number and percentage of participants with TEAEs per the following classifications:

- Participants with any TEAEs
- Participants with Treatment-Emergent Drug-Related AEs
- Participants with Treatment-Emergent AEs by Maximum Severity as Mild, Moderate, and Severe.
- Participants with TEAE leading to discontinuation from study
- Participants with Treatment-Emergent SAEs
- Participants with Treatment-Emergent SAEs leading to discontinuation from study
- Participants with Treatment-Emergent SAEs resulting in death

The following summary tables for TEAEs will be presented:

- Number and percent of participants reporting treatment-emergent AEs, grouped by MedDRA system organ class and preferred term
- Number and percent of participants reporting treatment-emergent drug-related AEs, grouped by MedDRA system organ class, and preferred term
- Number and percent of participants reporting treatment-emergent AEs, grouped by MedDRA system organ class, preferred term, and maximum severity
- Number and percent of participants reporting treatment-emergent SAEs will be tabulated by system organ class and preferred term and presented by treatment.
- Number and percent of participants reporting treatment-emergent AEs leading to study discontinuation, grouped by MedDRA system organ class and preferred term

For the summary tables above, the SOC terms and PTs will be presented in decreasing order of the total number of participants (frequency) who experienced each AE. System organ class terms and PTs with the same frequency will be presented alphabetically. In the case of multiple occurrences of the same TEAE within the same participant, each participant will only be counted once for each preferred term.

The following data listings for AEs will be provided for each participant by displaying the events captured on the CRF:

- All AEs,
- All serious AEs,
- All AEs leading to study discontinuation, and
- All AEs leading to Death.

In the AE data listings, all AEs will be displayed. AEs that are not treatment-emergent will be flagged in the AE listings.

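### The SAP tabulates disposition, demographics and AEs by treatment in a one-treatment study: define the columns by prior randomised arm plus Total, and reconcile the two TEAE rules

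*SAP*

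**What the plan says.** The SAP groups its output by treatment almost everywhere. Section 7.1 introduces disposition with "The following will be summarized by treatment group", and section 7.2 treats demographics the same way. Section 9.1.4 says "An overall summary of TEAEs will be provided by treatment" and also presents the SAE table by treatment. Section 6.1.6 refers to treatment received, section 9 says "For all safety and tolerability analyses, participants will be analyzed by the actual treatment", and section 12.3 sorts listings by treatment. Percentages in section 4.1 are generally based on "the total number of subjects in the study population for the treatment group (or cohorts), unless otherwise specified".

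There is, however, only one treatment. Section 3.4 states: "All participants received simufilam 100 mg tablets BID". Section 3.5 repeats this and calls the study non-randomised. Neither treatment group nor cohort is defined, and no table title in sections 12.1 and 12.2 names a prior-arm split. The one prior-arm analysis in the SAP, HbA1c shifts, is among those that section 10 drops because of early termination by the sponsor.

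The SAP gives two rules for AEs that predate the first dose. Section 6.1.6: "Ongoing AEs from the pivotal studies will be classified as TEAEs in the current study only if they increase in severity"; otherwise they become medical history. Section 9.1 counts such an event if "it increased in severity or became serious on or after the date of the first dose of study drug".

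**The concern.** The participants differ by design. Protocol 2.3 describes PTI-125-06 as a 76-week study of placebo, 50 mg and 100 mg, and PTI-125-07 as a 52-week study of placebo and 100 mg. Former placebo patients meet simufilam for the first time in this extension. The others were assigned to it for 52 or 76 weeks beforehand. AE incidence is the only safety endpoint in SAP 2.2.1, and section 10 removes laboratory values, vital signs, weight, ECG, C-SSRS and HbA1c. If AEs sit in one column, no listed table separates starting the drug from continuing it.

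The two TEAE rules matter whatever the column layout. An AE carried over from a parent study that becomes serious without a change in severity grade is medical history under section 6.1.6 and a treatment-emergent SAE under section 9.1. Which rule is programmed decides whether it enters the SAE table.

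**Working it through.** The plan states no sample size, power or rate that could be reproduced (SAP 3.2). The check therefore has three parts: the text, an illustration of what pooling can hide, and the two TEAE rules.

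**1. Number of columns.** Grouping by actual treatment (section 9), with one regimen for everyone (sections 3.4 and 3.5), gives one group. The reference to cohorts in section 4.1 does not change this, because none is defined. The shells are not among the documents, so the single column is inferred from the SAP text and table list.

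**2. Illustrative make-up of that column.** Inputs: 1,081 participants (SAP 3.3); about 1,083 subjects in three arms and about 750 in two arms (Protocol 2.3). Equal allocation and equal rollover are assumptions.
- Placebo: 1,083/3 + 750/2 = 361 + 375 = 736. The 100 mg arms also total 736. 50 mg: 361. Sum: 1,833.
- Scaled to 1,081: 1,081 × 736/1,833 = 434 (40.2%) for placebo and for 100 mg; 1,081 × 361/1,833 = 213 (19.7%) for 50 mg.
- Parent-study mix, rollover equal across arms: if nearly all came from PTI-125-06, the placebo share is 1/3, or 360. If all 750 of PTI-125-07 entered, it is 375 + (1,081 − 750)/3 = 375 + 110 = 485, or 45%.
- Rollover differing by arm, study mix as above: if the simufilam arms enter at r times the placebo rate, the share is 736/(736 + 1,097r). At r = 0.8 this is 45.6%; at r = 1.25 it is 34.9%. Varying both widens the range.

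**3. What pooling can hide.** Pooled rate = s × p(first) + (1 − s) × p(continued). With assumed rates of 10% and 2%:

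| Former-placebo share s | Pooled rate |
|---|---|
| 33.3% | 4.7% |
| 40.2% | 5.2% |
| 44.9% | 5.6% |

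A uniform rate of 5.2% in everyone would produce the same middle figure. With equal rates in the groups nothing is diluted.

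**4. What the split could resolve.** The 95% half-width for a difference of 434 versus 434 is 1.96 × √(2p(1 − p)/434): 1.9 points at p = 2%, 2.9 at 5% and 4.0 at 10%. With zero events, the one-sided 95% upper bound 1 − 0.05^(1/n) is 0.69% for n = 434, 1.40% for n = 213 and 0.28% for n = 1,081.

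**5. The TEAE rules side by side**, for an AE that began in a parent study and is ongoing at first dose:

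| Course after first dose | Section 6.1.6 | Section 9.1 |
|---|---|---|
| Unchanged | Medical history | Not a TEAE |
| Severity increases | TEAE | TEAE |
| Becomes serious, same severity | Medical history | TEAE |

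The third row is a contradiction. The documents do not give the number of AEs ongoing at rollover, so its effect on the counts cannot be sized.

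**The case against.** The strongest reply is that nothing the plan promises fails. The objective (Protocol 3, SAP 2.1.1) is long-term safety and tolerability, and SAP 2.2.1 defines incidence without a split. Protocol 12.2 asks for no AE split by prior arm; Protocol 12.3 to 12.5 reserve prior-arm cohorts for HbA1c, biomarkers and CDR. The study is exploratory, its reporting was cut after early termination, and SAP section 1 allows labelled post-hoc analyses. All of this stands. It makes the column point an improvement in reporting.

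A reader might infer that the SAP departs from the protocol on AEs, or that the pooled incidence is invalid or conceals a known signal. The documents support none of these. They give no AE rates by prior arm, and the randomised parent trials are the better source on AEs at the start of treatment.

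A reader might also expect the split to isolate the effect of first exposure. It would not. Every entrant had to complete a parent study and pass the exclusions for earlier AEs (Protocol 5.2 and 5.3), but only former simufilam patients did so on drug. Prior 50 mg comes only from the 76-week study, while placebo and 100 mg come from both, so arm is mixed with parent study and duration. Differential loss by arm is possible but not documented.

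On the TEAE rules, it can be argued that section 6.1.6 is the specific provision and section 9.1 the general one. The SAP sets no such precedence, and both cover the same events.

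**Conclusion.** The concern holds in two parts of different weight. First, the grouping term is undefined for a single-treatment study, and prior-arm columns would be a cheap gain in interpretability. Their absence does not undermine the pooled result. The illustrative size is a former-placebo share of about 40% under equal allocation and rollover, about 33% to 45% from parent-study mix alone, and wider if rollover differs by arm. The 10% and 2% AE rates serve only to show the mechanism. The single-column layout rests on the SAP text and could be overturned by shells that already carry prior arm; a sentence defining the columns would then suffice.

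Second, sections 6.1.6 and 9.1 conflict on ongoing AEs that become serious. This is an error as written and depends on no assumption about layout or rates.

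**What to change.** - Define the columns of Tables 14.1.1, 14.1.2 and 14.3.1.1 to 14.3.1.6 as prior randomised treatment (placebo, 50 mg, 100 mg) plus Total, each with its own denominator.
- Label the contrast descriptive, open-label and among parent-trial completers, and footnote which parent studies feed each column.
- Summarise the gap between the last parent-study dose and Study Day 1. SAP 6.1.1 provides for cases where the End-of-Treatment visit and "the Study Day 1 visit for the open-label extension study did not occur on the same date", so prior 100 mg does not guarantee continuous exposure. A re-entry gap summary is needed only if any subject re-entered: the SAP is written to protocol version 3.0 as a 52-week study and has no re-entry visits.
- State one TEAE rule in sections 6.1.6 and 9.1, under which an ongoing AE that becomes serious is not classed as medical history.
- If the database is already locked, produce the prior-arm tables labelled post-hoc, as SAP section 1 permits.

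The cost is SAP wording, three extra columns and one gap summary, with no new patients. The prior-arm variable should be available, since Protocol 12.3 and 12.5 already plan analyses by it. The downside is wider tables and smaller counts per column; the Total column keeps the pooled precision.

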#### 9.1. Adverse Events

An AE is any undesirable event that occurs to a participant during a study, whether that event is considered related to Study Drug.

All summaries of AEs will be based on treatment-emergent adverse events (TEAEs) unless specified otherwise.

An adverse event is considered a TEAE if:

• The adverse event first occurred on or after the date of the first dose of study drug; or

• The adverse event was before the date of the first dose of study drug, but it increased in severity or became serious on or after the date of the first dose of study drug.

# 9.1.1. Severity of Adverse Events

The severity of each AE should be characterized and then classified into one of three clearly defined categories as follows:

- Mild
- Moderate
- Severe

These three categories are based on the Investigator's clinical judgment, which in turn depends on consideration of several factors such as the participant's report and the physician's observations.

The missing severity of an AE will be imputed to "severe".

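### SAP 9.1.1 does not limit its impute-as-severe rule to on-study grades; applied to a missing pre-dose grade, it blocks the severity-increase route to TEAE status for carried-over AEs

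*SAP*

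**What the plan says.** SAP 9.1.1 puts each AE on a three-level scale (mild, moderate, severe) and adds: "The missing severity of an AE will be imputed to 'severe". It does not restrict this to TEAEs, to on-study grades or to the maximum-severity table. Nor does it say whether imputation comes before or after treatment emergence is decided.

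Two sections decide when an AE that began before the first dose counts as a TEAE:

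- SAP 9.1 counts it if "it increased in severity or became serious on or after the date of the first dose of study drug".
- SAP 6.1.6, which deals with AEs ongoing from the phase 3 studies, counts it "only if they increase in severity on or after the date of the first dose of study drug in the current study". For the rest it says: "Otherwise, they will be classified as medical history events".

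On reporting, SAP 9.1 says: "All summaries of AEs will be based on treatment-emergent adverse events (TEAEs) unless specified otherwise". An event that fails the test therefore leaves the summary tables. SAP 9.1.4 adds a safeguard for the listings: "AEs that are not treatment-emergent will be flagged in the AE listings".

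**The concern.** Imputing the worst grade is meant to avoid understating harm. For an on-study grade it does so. For a starting grade it does the opposite, because a change is judged against that grade and nothing lies above severe. Severe is also an unlikely true starting grade here: Protocol 5.3, exclusion 8, removes subjects whose ongoing moderate or severe AE is judged a potential safety risk.

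This is a rollover study, so ongoing AEs at entry are expected, and 6.1.6 has a rule for them. AE incidence and severity are the only endpoint in SAP 2.2.1, and SAP 10 drops the laboratory, vital-sign, ECG and C-SSRS analyses. Whatever misclassifies a TEAE therefore acts on the only safety result left.

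An event refiled as medical history may also be hard to find. SAP Table 4 names no medical-history listing, and its by-subject AE listing is titled as treatment-emergent. However, 9.1.4 promises all AEs with a flag, and 12.3 speaks in general of one listing per CRF domain.

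**Working it through.** The plan states no figure for this point, so there is none to reproduce. The check applies the rules literally.

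**Inputs.** Three ordered grades and missing set to severe (SAP 9.1.1); the two TEAE rules (SAP 9.1 and 6.1.6); 1,081 participants (SAP 3.3). Score mild = 1, moderate = 2, severe = 3, missing = 3. Severity has increased if the post-dose score exceeds the pre-dose score.

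**Step 1: pre-dose grade missing (score 3).**

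| Post-dose grade | Increase? | TEAE under 9.1, not serious | TEAE under 9.1, became serious | TEAE under 6.1.6 |
|---|---|---|---|---|
| Mild | 1 > 3: no | no | yes | no |
| Moderate | 2 > 3: no | no | yes | no |
| Severe | 3 > 3: no | no | yes | no |
| Missing | 3 > 3: no | no | yes | no |

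An increase registers in 0 of 4 states. The became-serious route works in 4 of 4 states under 9.1 and in none under 6.1.6.

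**Step 2: true worsening.** The paths are mild to moderate, mild to severe and moderate to severe. With the pre-dose grade missing, the comparisons are 2 > 3, 3 > 3 and 3 > 3, so 0 of 3 are detected.

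**Step 3: missing pre-dose grade taken as mild (score 1).** The same paths give 2 > 1, 3 > 1 and 3 > 1, so 3 of 3 are detected. Of the 6 paths without worsening, 3 are also flagged: moderate to moderate, severe to moderate and severe to severe. The other 3 end at mild and are not flagged.

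**Step 4: size.** The documents give neither the number of carried-over AEs nor the rate of missing grades. Assume 200 to 600 carried-over AEs, 0.2% to 2% with a missing pre-dose grade, and 10% to 20% that worsen on drug:

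- low: 200 × 0.002 × 0.10 = 0.04 worsening events lost
- high: 600 × 0.02 × 0.20 = 2.4 worsening events lost; 2.4 / 1,081 = 0.22%

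Free of those assumptions, k affected participants with no other TEAE move the overall TEAE percentage by 100 × k / 1,081. That is 0.09 points for k = 1, 0.46 for 5, 0.93 for 10 and 1.85 for 20.

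**The case against.** The strongest reply is that 9.1.1 never mentions a pre-dose grade and does not say that imputation precedes the TEAE derivation. A programmer might decide emergence first and impute afterwards only for the severity tables. Grades for carried-over AEs may also come from the phase 3 databases, whose handling of missing grades is not visible here. This stands in part: the harmful order is an inference. But it is the literal reading of an unrestricted sentence, and nothing in the SAP prevents it.

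A reader might infer that such an event can never be a TEAE and that its worsening is always lost. The documents do not support that, for two reasons:

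- SAP 9.1 still counts it if it becomes serious. Section 6.1.6 omits that route, and the SAP does not say which section governs.
- Protocol 11.1 treats worsening of a pre-existing condition as an AE in itself. If it is entered as a new record with on-study onset, the first TEAE criterion in SAP 9.1 counts it without any pre-dose grade. The SAP does not say how such records are linked, so this softens the problem without removing it.

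A reader might also object that the rule creates false severe TEAEs when the on-study grade is missing. That is not a defect: counting an unknown on-study grade as severe is the over-count that a worst-case rule intends. Taking it instead as unchanged from the pre-dose grade would miss all 3 worsening paths, which the current rule catches when the pre-dose grade is known.

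Finally, the numbers should be small. Protocol 11.2 calls for severity to be recorded in EDC, and Protocol 14.1 requires the data to be verified before lock. The study is single-arm and exploratory, and no decision rule depends on the count. This stands, and it limits the weight of the point.

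**Conclusion.** The point holds in a limited form. Applied as written to a missing pre-dose grade, the imputation closes the severity-increase route to TEAE status. That leaves only the became-serious route, on which 9.1 and 6.1.6 disagree. On-drug worsening of such an event is then undercounted in the TEAE tables unless it is recorded as a new on-study event.

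This rests on two assumptions: that imputation is done before emergence is derived, and that some carried-over AEs lack a pre-dose grade. The size is unknown and probably very small, at most about 2.4 events under the assumed ranges. It is a minor correction to a rule that works against its own purpose, and it does not threaten the study's safety conclusions.

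**What to change.** In SAP 9.1.1, add that when treatment emergence of a pre-existing AE is decided, a missing pre-dose severity is taken as mild, and a missing severity on or after the first dose remains imputed as severe. In SAP 6.1.6, add the became-serious route so that the section agrees with 9.1. Report in the CSR how many records the rule touched.

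The cost is a few sentences and a small change in the derivation; no new data are needed. The downside is over-counting: some events with an unknown starting grade that did not worsen will become TEAEs, and one with no grade at either time will count as a severe TEAE. Under the same assumed ranges, events with a missing pre-dose grade number 200 × 0.002 = 0.4 to 600 × 0.02 = 12. The additions, true and false together, therefore cannot exceed 12 events (12 / 1,081 = 1.11%). That errs towards counting harm, as the present rule intends. If the database is already locked, the CSR should state the derivation order used and show the alternative as a sensitivity count.
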